3.1.2.1 Safety Evaluation Phase of BMS-986158 Monotherapy Expansion

Clinical safety monitoring of subjects treated with BMS-986158 monotherapy enrolled in Part 2 of the study will be the same as conducted during the dose escalation portion. During Part 2, if in a given tumor cohort the combined incidence of study drug-related AEs that require dose modification exceeds 29% (of treated subjects), then further enrollment to that arm may be interrupted and the findings will be discussed between the Sponsor/Medical Monitor and investigators. An agreement will be reached as to whether a lower dose level or an alternate dose schedule of BMS-986158 should be examined, or whether any additional treatment guidelines should be implemented prior to enrollment of additional subjects on study in alignment with dose modification criteria (Section 4.5.2), discontinuation criteria, and other safety evaluation criteria.

3.1.2.2 Safety Evaluation Phase of BMS-986158 Combination with Nivolumab

If combination therapy with nivolumab is pursued, the safety of the selected BMS-986158 dose when given in combination with nivolumab within the dose expansion phase will be evaluated by monitoring DLTs in the first 6 to 12 subjects treated across the different tumor cohorts receiving combination therapy. Once the selected dose of BMS-986158 in combination with nivolumab is deemed safe based on the DLT evaluation, the dose expansion will continue as planned in all cohorts.

The guidance for assessing the DLT-related safety and overall safety will be similar to that used in the monotherapy cohorts. The DLT safety monitoring during the dose evaluation phase including potential decision to de-escalate to a lower dose will be based on the mTPI-2 design⁴⁹ with target toxicity (DLT) rate of 29% (-2%, +4%), as presented in Table 3.1.2.2-1. The performance of the design is reported in Appendix 8.

Initially, the first 3 to 4 subjects treated in combination will be evaluated for DLT. If 0 or 1 DLT is observed during the DLT period established for BMS-986158, an additional 3 subjects will be treated at the same BMS-986158 dose level. A decision to stay at the same dose level by treating additional 3 to 4 subjects, to expand (continue enrollment) of all subjects treated with combination therapy across all tumor cohorts (declaring this dose to be safe), or to consider de-escalation will be guided by the number of subjects with DLTs observed during the dose evaluation phase and the posterior probability of DLT. (Table 3.1.2.2-1 and Table 3.1.2.2-2). Subjects who do not complete the DLT observation period for reasons other than DLTs will not contribute to this safety evaluation and can be replaced. De-escalation may be considered if the safety and tolerability

profile for the selected BMS-986158 dose is evaluated as not acceptable, after discussion between the investigator(s) and the Sponsor/Medical Monitor.

Evaluation					se by m						
			N	umber o	f DLT Ev	aluable P	articipan	ts Treate	d		
Ľ		3	4	5	6	7	8	9	10	11	12
a DLT	0	Е	Е	Е	Е	Е	Е	Е	Е	Е	Е
	1	Е	Е	Е	Е	Е	Е	Е	Е	Е	Е
nts v	2	D	D	D	S	Е	Е	Е	Е	Е	Е
cipaı	3	DU	D	D	D	D	D	S	S	Е	Е
parti	4	-	DU	DU	D	D	D	D	D	D	S*
r of]	5	-	-	DU	DU	DU	DU	D	D	D	D
Number of participants with	6	-	-	-	DU	DU	DU	DU	DU	D	D
Nu	7	-	-	-	-	DU	DU	DU	DU	DU	DU

Combination Safety Monitoring Guidance for DLT during Safety Table 3.1.2.2-1:

Source: Target Toxicity (DLT) Rate used is 29% (-2%, +4%).

D = de-escalate to lower dose; DLT = dose limiting toxicity; E = expand at this dose in each tumor type; DU = de-escalate to lower dose and the current dose will never be used again in the trial; mTPI = modified Toxicity Probability Interval; S = stay at the same dose.

*Additional considerations including information from Table 3.1.2.2-2 below will be used.

In the case where 4 DLTs are observed out of 12 evaluable subjects as shown in Table 3.1.2.2-1, the design recommends the decision to stay at the same dose level (S), indicating that more subjects need to be evaluated to determine whether the dose level is safe. After considering additional information such as provided in Table 3.1.2.2-2, a lower dose may be considered for evaluation based on discussion between Sponsor/Medical Monitor and investigators.

In addition to the above guidance, the following posterior probabilities may be utilized to make a more informed decision on the safety based on DLT findings prior to the decision to expand. Assuming a 33% acceptable DLT rate in a combination therapy setting, which corresponds to a Beta(1,2) distribution, Table 3.1.2.2-2 shows the risk of selecting a BMS-986158 dose level as safe based on the observed DLTs and expressed as a posterior probability of toxicity given the number of DLTs observed during the combination safety evaluation phase.

Table 3.1.2.2-2:	Posterior Probability of a DLT in Combination Therapy Assuming
	Observed Data

Number of Subjects at a Dose Level	Number of Subjects with an Observed DLT	Probability of DLT Rate >33%	Probability of DLT Rate >40%
6	0	4%	2%
6	1	20%	11%
6	2	47%	32%

Revised Protocol No.: 07 Date: 18-Mar-2019

Number of Subjects at a Dose Level	Number of Subjects with an Observed DLT	Probability of DLT Rate >33%	Probability of DLT Rate >40%
9	1	8%	3%
9	2	24%	12%
9	3	48%	30%
12	2	11%	4%
12	3	27%	12%
12	4	48%	28%

Table 3.1.2.2-2:Posterior Probability of a DLT in Combination Therapy Assuming
Observed Data

Posterior probabilities are calculated using a Beta(1,2) prior corresponding to 33% DLT rate (ie, 1 of 3 evaluable subjects has a DLT).

DLT = dose limiting toxicity.

Based on the above, if 0 out of 6, 1 out of 9, or 2 out of 12 subjects experience a DLT, the dose level may be considered sufficiently safe to open enrollment to the additional subjects in the expansion phase of the study.

3.1.2.3 Safety Evaluation in Adolescents

Adolescent subjects will be treated with a dose and schedule selected from Part 1 (dose escalation) in adult subjects. The safety of this selected BMS-986158 dose will be evaluated in adolescents $(\geq 12 \text{ to } < 18 \text{ years of age})$ as part of the dose expansion phase (Part 2) in subjects with NMC, BL. ES, or other tumors with genetic abnormalities in BRD proteins (Section 1.1.7 and Section 1.1.13). Initially, 3 to 4 adolescent subjects across different tumor types may be enrolled in the Initial Expansion and monitored for DLT. Further enrollment of adolescent subjects into the Subsequent Expansion will depend on the totality of data, including safety, PK and PD data obtained from all subjects in the initial expansion. Based on safety and other available data, the Sponsor may consider decreasing the dose level of BMS-986158 for adolescent subjects. The selected dose may be further evaluated in adolescent subjects in combination with nivolumab, if combination therapy is pursued, depending on the review of pharmacodynamics results and other data from BMS-986158 monotherapy. If pursued, 3 to 4 subjects ≥ 12 to < 18 years of age across any eligible tumor types (eg, NMC, BL, and ES), will be treated with BMS-986158 in combination with nivolumab to establish safety of the combination treatment in this adolescent population. Subjects will be observed for DLT, and if safety is considered acceptable, additional adolescent subjects will be treated with combination therapy.

MYC AMPLIFICAT	IONS			
Non-GC-DLBCL	5 to 9	5 to 9	5 to 9	15 to 27
OC w MYC amplifications		5 to 9	5 to 9	10 to 18
UCS		5 to 9	5 to 9	10 to 18

Table 3.1.2.4-1:Dose Expansion Planned Sample Size

Tumor Cohort and Group	Initial Monotherapy	Subsequent Monotherapy	Combination Therapy	Total
AR AMPLIFICATIO	NS			
CRPC	5 to 9	5 to 9	5 to 9	15 to 27
MUTATIONS				
RCC		5 to 9	5 to 9	10 to 18
NSCLC		5 to 9	5 to 9	10 to 18
UM		5 to 9	5 to 9	10 to 18
All Cohorts	25 to 45	70 to 126	70 to 126	165 to 297

Table 3.1.2.4-1:	Dose Expansion Planned Sample Size
------------------	---

The minimum overall planned sample sizes are based on Stage 1 initial enrollment, subsequent enrollment, and combination therapy enrollment subject counts per cohort. The maximums are determined similarly. The above assumes that the selected dose level administered in combination is deemed safe; alternately an additional 6 to12 subjects may need to be treated to assess safety at a lower dose level and to continue enrolling all combination therapy cohorts.

An additional 6 to 12 subjects may be enrolled to evaluate a lower dose of BMS-986158 in combination therapy as well as another 18 subjects may be enrolled to evaluate target gene engagement in tumors, and additional PK and safety characteristics in up to 2 cohorts at a different dose or schedule. Therefore, the potential total for expansion will be approximately up to 201 subjects if only monotherapy is pursued, and approximately up to 327 subjects if all planned expansion cohort subjects in monotherapy and combination therapy groups are pursued.

Administration of Additional Treatment Cycles:

Subjects may discontinue treatment due to disease progression, unacceptable AEs, or at the subject's request. Treatment decisions related to subject management will be based exclusively on RECIST version 1.1 (Appendix 4), the Lugano 2014 criteria (Appendix 9), or PCWG3 criteria (including PSA assessments) (Appendix 12). Subjects with an objective response of CR, partial response (PR) or stable disease, will continue therapy until they develop progressive disease (PD, unless in case of treatment beyond progression as detailed in Section 3.6), experience clinical deterioration, develop AEs requiring discontinuation of treatment or withdraw consent. Subjects who developed disease progression on BMS-986158 monotherapy in Part 2 will not be allowed to switch to combination therapy.

Subjects who develop toxicity requiring discontinuation of treatment will enter the Clinical Follow-up Period. The subject should be seen in follow-up at least every 30 days, until the AE has resolved to baseline, stabilized, or been deemed irreversible. After completion of the Clinical Follow-up Period, subjects will then enter the Survival Follow-up Period. During this period, clinic visits or telephone contact every 3-4 months will be performed to assess survival status.

Revised Protocol No.: 07 Date: 18-Mar-2019 The end of the study will occur after the last treated subject completes their Clinical Follow-up unless if a subject discontinues prematurely. Subjects in Survival Follow-up Period who have progression of disease will be eligible to receive anticancer therapy as appropriate.

3.2 Post Study Access to Therapy

At the end of the study, BMS will not continue to provide BMS supplied study drugs to subjects/investigators unless BMS chooses to extend the study. The investigator should ensure that the subject receives appropriate SOC to treat the condition under study.

3.3 Study Population

Subjects will undergo screening evaluations to determine eligibility within 28 days for Part 1 and up to 40 days for Part 2 prior to first administration of study medication. For entry into the study, the subject MUST fulfill the required eligibility data prior to dosing on Day 1. No exceptions will be granted.

3.3.1 Inclusion Criteria

1) Signed Written Informed Consent

- a) The subject must sign the informed consent form prior to the performance of any study related procedures that are not considered part of standard of care.
 - i) Part 2 only: Subjects must consent and will be required to undergo mandatory pretreatment and on-treatment biopsies. Adolescent subjects with genetic alterations detected as SOC (eg, IGH/MYC fusion) are exempt from this requirement. Subjects must have a lesion that can be biopsied at acceptable clinical risk as judged by the investigator. Subjects whose pre-treatment biopsy yields inadequate tissue quantity or quality will be eligible if sufficient archival tissue is available, after discussion with the Medical Monitor. For subjects with adequate pretreatment biopsy and available archival tissue, both specimens should be submitted. Existing formalin-fixed paraffin-embedded (FFPE) tumor tissue, either a block or unstained slides (minimum 20 slides are required) for performance of correlative studies, should also be collected if available. Additional information concerning the number of tissue cores and preparation are provided in the Laboratory Manual.

2) Target Population

a) Subjects must have a confirmed histologic or cytologic diagnosis of one of the following malignancies for participation in the study and meet the other criteria listed (a specific exception for disease diagnosis criteria is noted in inclusion criterion k and requirements for the test are noted in inclusion criterion m)

i) Ovarian cancer (OC)

(1) Histological or cytological documented epithelial ovarian cancer, primary peritoneal carcinoma, or fallopian tube cancer

- (2) Received at least one prior Platinum Based Therapy (PBT) regimen
- (3) Have platinum-resistant/refractory disease (progression or recurrence within 6 months), be intolerant of platinum-containing compounds, and/or have hypersensitivity to platinum-containing compounds.
- (4) Must have known BRCA1/2 mutation status, and if BRCA1/2 mutation is present, must have received treatment with a PARP inhibitor, if available
- (5) For Part 2 Expansion only: All OC subjects must have BRD and/or MYC amplification in tumor cells

ii) Triple negative breast cancer (TNBC)

- (1) Males and females with histologically or cytologically confirmed triple negative breast carcinoma as defined by ASCO/CAP guidelines.
- (2) Had progression or refractory disease during or after at least 1 chemotherapy regimen for the treatment of metastatic or locally advanced disease.
- (3) Part 2 only: all subjects with TNBC must have BRD amplification in tumor cells

iii) Part 1 only: Small cell lung cancer (SCLC)

- (1) Histologically or cytologically documented SCLC, limited or extensive stage disease.
- (2) Received at least 1 prior Platinum Based Therapy (PBT) regimen.

iv) Part 2 only: Non-Small cell lung cancer (NSCLC)

- (1) Histologically or cytologically documented NSCLC
- (2) Had progression during or after at least 2 lines of therapy in the advanced metastatic setting
- (3) Subjects must have mutations in SWI/SNF complex in tumor cells or detected KRAS mutation with wild type STK11 in tumor cells
- (4) Subjects must have received at least 1 prior checkpoint inhibitor immunotherapy
- (5) Subjects with known abnormalities of EGFR, ALK, ROS1, BRAF must have received appropriate targeted therapies
- (6) Subjects should be ineligible for or received a platinum-based chemotherapy for NSCLC in the adjuvant, neoadjuvant, or recurrent setting

v) Part 2 only: Renal cell carcinoma (RCC)

- (1) Histologically or cytologically confirmed metastatic RCC
- (2) Detected mutations in SWI/SNF complex in tumor cells
- (3) Had progression or refractory disease during or after at least 2 lines of therapy

vi) Part 2 only: Uveal melanoma (UM)

- (1) Histologically or cytologically confirmed unresectable or metastatic UM
- (2) Detected Gnaq/11 mutations in tumor cells

(3) Untreated or had progression or refractory disease during or after any line of therapy

vii) Part 2 only: Uterine carcinosarcoma (UCS)

- (1) Women with histologically or cytologically confirmed UCS
- (2) Detected MYC amplifications in tumor cells
- (3) Had progression or refractory disease during or after at least 1L treatment regimen

viii) Part 2 only: Neuroendocrine prostate cancer (NEPC)

- (1) Men with histologically or cytologically confirmed unresectable or metastatic NEPC
- (2) Detected BRD amplification in tumor cells
- (3) Had progression or refractory disease during or after at least 1L treatment regimen

ix) Part 2 only: Castration-resistant prostate cancer (CRPC)

- (1) Men with histologically or cytologically confirmed unresectable or metastatic CRPC
- (2) Detected AR amplification in tumor cells (with or without MYC amplification)
- (3) Had progression or refractory disease during or after at least 1 treatment with a taxane and with an androgen pathway antagonist (eg, abiraterone or enzalutamide). Abiraterone but not enzalutamide may be continued during the study.
- (4) Detected MYC amplification in tumor cells (with or without AR amplification)

x) Part 2 only: NUT-midline carcinoma (NMC)

- (1) Adult and adolescent subjects with Fluorescence in situ hybridization (FISH)confirmed fusion of NUT with BRD3 or BRD4
- (2) Unresectable, or had progression or refractory disease during or after any line of therapy

xi) Part 2 only: Ewing sarcoma (ES)

- (1) Adult and adolescent subjects with FISH-confirmed fusion of EWS with FLI1
- (2) Had progression or refractory disease during or after at least 1L chemotherapy regimen

xii) Part 2 only: Burkitt's lymphoma/leukemia (BL)

- (1) Adult and adolescent subjects with FISH-confirmed rearrangement of MYC
- (2) Had progression or refractory disease during or after at least 1L chemotherapy regimen
- (3) Confirmed presence or absence of bone marrow involvement before enrollment.

xiii) Part 2 only: Double-hit lymphoma (DHL) or non-germinal center subtype of diffuse large B-cell lymphoma (non-GC-DLBCL)

(1) FISH-confirmed rearrangement of MYC and of BCL2 or BCL6 DHL

- (2) Had progression or refractory disease during or after at least 1 chemotherapy regimen
- (3) Confirmed presence or absence of bone marrow involvement before enrollment
- (4) IHC confirmed CD 10-, BCL6- DLBCL, or CD10-, BCL6+ and MUM1+ DLBCL. Gene expression profile may also be used to confirm a diagnosis of non-GC-DLBCL
- **xiv) Part 2 only**: adolescent subjects with malignancies harboring genetic abnormalities likely sensitive to BET inhibition who have progressive disease with no effective therapeutic options may be enrolled after discussion and agreement between the Sponsor/Medical Monitor and Investigator.
- b) Subjects with controlled, treated brain metastasis fulfilling all the following criteria may be screened: no radiographic progression for at least 2 weeks following radiation and/or surgical treatment, off steroids for at least 2 weeks, without new or progressing neurological signs or symptoms.
- c) All subjects must have at least one measurable lesion at baseline by computed tomography (CT) or magnetic resonance imaging (MRI) as per RECIST v1.1 for solid tumors or Lugano 2014 criteria for lymphomas.
- d) For Part 1, all subjects must have archival tumor tissue identified and available (if slides are provided, a minimum of 10 (ten) unstained slides with at least 5 micron thick tissue sections are required) **unless a fresh biopsy is provided.** All subjects not providing a fresh biopsy must consent to provide tumor blocks or slides to the sponsor and the availability of the tissue must be confirmed prior to subjects receiving study medication. If an archived tumor specimen is unavailable or unsuitable for this study if it can be performed at minimal acceptable clinical risk as judged by the investigator and if it does not include a target lesion or lesion in an area treated with prior radiation therapy.

For Part 2, both a pre-treatment and on-treatment fresh biopsy must be provided. EOT biopsies must be collected for subjects experiencing PD. For adolescent subjects, fresh biopsies pre- and post-treatment are preferred but not mandated. If a fresh biopsy is not provided, archival tumor tissue is required. The screening tumor tissue for the expansion cohorts enrolled in Part 2 of the study must be shipped as described in the laboratory manual for biomarker testing including identification of select pre-defined genetic biomarkers prior to treatment, with the exception of samples from subjects with NMC, ES, BL, and DHL for which the characterization of fusion proteins is a part of SOC. Subjects whose pre-treatment biopsy yields inadequate tissue quantity or quality will only be eligible if sufficient archival tissue is available, after discussion with the Medical Monitor. If there is only 1 measureable lesion and a core needle biopsy is done (instead of excisional), the lesion may be used as a measureable lesion. If there are more than 1 measureable lesions, the lesion being biopsied should not be a target lesion. Fine needle biopsies are not allowed.

e) Subjects must have a life expectancy of at least 3 months.

- f) Subjects must have an Eastern Cooperative Oncology Group (ECOG) Performance Status of 0 to 1 (Appendix 5).
- g) Subjects who have undergone any major surgery within 4 weeks of study drug administration are excluded. Subjects must have recovered from the effects of major surgery at least 14 days before the first dose of the study drug.
- h) Prophylactic anticoagulation for venous access devices with low-dose heparin or similar (e.g. heparin catheter flush) will be permitted.
- i) For antiplatelet agents, prophylactic doses are permitted (e.g. aspirin < 300 mg daily, clopidogrel < 75 mg daily).
- j) Subject Re-enrollment: This study permits the re-enrollment of a subject that has discontinued the study as a pre-treatment failure (ie, subject has not been treated). If re-enrolled, the subject must be re-consented.
- k) Subjects with solid tumor types that are not included in the preferred target population may also be enrolled after a minimum of 2 subjects with the preferred tumor types have been enrolled at a single dose level during escalation, or during monotherapy expansion after discussion with the Sponsor/Study Director. These subjects must have progressed on or had refractory disease to at least one prior anticancer regimen, not be eligible for additional effective standard of care therapy for their disease, and must have the possibility of being positively impacted by the treatment offered in this study.
- 1) Androgen Receptor Deprivation (ARD) therapy is permitted for subjects with prostate cancer at doses defined by the investigator if the therapeutic agent is not a strong inducer or inhibitor of CYP3A4 activity.
- m) If biomarker result from the sector test is inconclusive, will repeat the test. If there is not enough tumor material, the tumor biopsy must be repeated. Subjects who have had prior tumor biopsy and analysis by conducted < 6 months prior to enrollment and have data available do not need to provide additional sample for testing at screening.

3) Previous Treatment

- a) Prior anticancer therapy treatments such as chemotherapy, radiotherapy, biological immunotherapy, or investigational agents (therapeutic or diagnostic) are permitted.
 - i) For cytotoxic agents, at least 4 weeks must have elapsed from last dose of prior cytotoxic anticancer therapy and the initiation of study drug administration.
 - **ii)** For non-cytotoxic agents, at least 4 weeks or 5 half-lives (whichever is shorter) must have elapsed from the last dose of prior non-cytotoxic anticancer therapy and the initiation of study drug administration. If 5 half-lives is shorter than 4 weeks, agreement with Sponsor/Medical Monitor is mandatory.
- b) *Not applicable; removed per Revised Protocol 03.* If subject had stem cell transplantation, the procedure must have occurred at least 3 months prior to treatment initiation (for autologous SCT) or 4 months (for allogeneic SCT) and without evidence of active graft-versus-host disease (GVHD).

- c) All acute toxicities, from any prior therapy (radiotherapy, chemotherapy, or surgical procedures) must have resolved to Grade ≤ 1, NCI CTCAE, version 4.03 or to baseline if irreversible.
- d) Concomitant therapy with bisphosphonates is acceptable as per American Society of Clinical Oncology (ASCO) guidelines. Doses of bisphosphonates must be stable for at least 30 days prior to treatment initiation, as per ASCO guidelines.

4) Age and Reproductive Status

- a) Males and Females, 12 years of age or greater at the time of informed consent.
 - i) For subjects < 18 years of age, age-adjusted normal ranges for all assessments shall be used, as appropriate, for inclusion, exclusion, and dose modification criteria. In addition, an alternate pediatric assessment (eg, left ventricular shortening fraction rather than left ventricular ejection fraction [LVEF]) with an institutionally defined normal range may be used as appropriate.
- b) Women of childbearing potential (WOCBP) must have a negative serum or urine pregnancy test (minimum sensitivity 25 IU/L or equivalent units of HCG) during screening and within 24 hours prior to the start of study drug.
- c) Women must not be breastfeeding
- d) WOCBP must agree to follow instructions for method(s) of contraception for the duration of treatment plus 5 half-lives of study treatments plus 30 days (duration of ovulatory cycle) for a total of 5 months post-treatment completion (see Appendix 11). In addition, female participants must be willing to refrain from donation of oocytes during this time.
- e) Males who are sexually active with WOCBP must agree to follow instructions for method(s) of contraception (Appendix 11) for the duration of treatment with study treatments plus 5 half-lives of study treatments plus 90 days (duration of sperm turnover) for a total of 7 months post-treatment completion. In addition, male participants must be willing to refrain from sperm donation during this time (see Appendix 11).
- f) WOCBP who are continuously not heterosexually active are exempt from contraceptive requirements, and still undergo pregnancy testing as described in this section.

Investigators shall counsel WOCBP and male subjects who are sexually active with WOCBP on the importance of pregnancy prevention and the implications of an unexpected pregnancy investigators shall advise on the use of highly effective methods of contraception. Highly effective methods of contraception have a failure rate of < 1% when used consistently and correctly.

One of the highly effective methods of contraception listed in Appendix 11 is required during study duration and until the end of relevant systemic exposure, which is defined as 5 months for females and 7 months for males.

Local laws and regulations may require use of alternative and/or additional contraception methods.

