- BRD: In patients with OC, BRD amplification is associated with worse overall survival.¹⁹ BRD gene amplification correlates with overexpression of BRD RNA (TCGA database) and is necessary for proliferation and survival of some tumor cell types, including OC²⁰ and triple negative breast cancer (TNBC).²¹ Blocking hyperactivity of BRD proteins with a BET inhibitor results in growth inhibition of xenografts obtained from patients with OC¹⁹ and from patients with TNBC.^{21,73,74} Approximately 43% of patients with TNBC, 55% of patients with neuroendocrine prostate cancer (NEPC), and 17% of patients with OC harbor BRD4 amplifications (TCGA database).
- MYC: Forty-one percent of patients with castration-resistant prostate cancer (CRPC) and 47% of OC patients harbor MYC amplifications (TCGA database). BET inhibition results in reduced MYC expression and inhibition of tumor growth in PDX models with high MYC expression and inhibition of AR signaling.⁷⁵ High frequency of MYC amplification (approximately 30%) has also been observed in patients with uterine carcinosarcoma (UCS; TCGA database). Also, the non-germinal center subtype of diffuse large B-cell lymphoma (non-GC-DLBCL) is often associated with MYC (and BCL2) overexpression.⁷⁶ A recent

Phase I study of a BET inhibitor in patients with relapsed and refractory lymphoma reported objective clinical responses in the non-GC-DLBCL subtype, in particular in patients with activated B cell (ABC)-DLBCL.⁷⁷

AR: Among other genetic abnormalities sensitive to BET regulation is AR amplification.²² AR promotes ligand-independent prostate cancer (PC) progression through c-MYC upregulation.⁷⁸ BET inhibitors decreased MYC levels and proliferation viability of CRPC cells, and inhibited growth of PC xenografts.²² Approximately 67% of CRPC patients harbor AR amplification, and 25% to 30% harbor both MYC and AR amplifications (TCGA database).

BRD, MYC, and AR amplifications will be detected in tumor biopsies using

diagnostic platform. Subjects with TNBC, non-GC-DLBCL and CRPC with any of these gene amplifications/overexpressions will be eligible to participate in Part 2 as part of the Initial Expansion. Subjects with other tumors with these amplifications may be eligible to participate in Part 2 of this study as part of the Subsequent Expansion based on review of the totality of data obtained from all subjects in the Initial Expansion in Part 2 (see Section 3.1.2 and Figure 3.1-1).

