in each of the cohorts, based on the Fleming (optimal) design criteria. Enrollment may continue after the initial 5 subjects to ensure that sufficient subjects are evaluable (eg, with tumor scans) or in case of early drop outs. In addition to futility, an efficacy boundary is shown (Table 8.1-2); however there will be no stopping due to an efficacy signal.

In summary, approximately up to 45 subjects are expected to be treated across the Initial monotherapy cohorts, with approximately 5 to 9 subjects per cohort (Table 8.1-2).

Table 8.1-2:Characteristics for Initial Monotherapy Expansion Cohorts Signal
assessment when guided by a Two-Stage Design

Tumor Cohort and Group	Target ORR %	SOC ORR %	Stage 1 / Total N	Stage 1 Res Futility/ Efficacy Boundary	Stage 2 Res Futility/ Efficacy Boundary	FPR/FNR (%)
FUSION PROTEINS						
NMC	50	10	5/9	0/2	2/3	10/10
DHL	50	10	5/9	0/2	2/3	10/10
BRD AMPLIFICATIONS						
TNBC	50	10	5/9	0/2	2/3	10/10
MYC AMPLIFICATIONS						
Non-GC-DLBCL	35	10	5/9	0/2	1/2	20/20
AR AMPLIFICATIONS						
CRPC	35	10	5/9	0/2	1/2	20/20

Abbreviations: CRPC = castrate-resistant prostate cancer; DHL = double-hit lymphoma; FNR = false negative rate; FPR = false positive rate; N = number of subjects; NMC = NUT-midline carcinoma; ORR = objective response rate; RCC = renal cell carcinoma; Res = response; SOC = standard of care; TNBC = triple negative breast cancer; Non-GC-DLBCL = Non-germinal center diffuse large B-cell lymphoma;

Note: Tumor ORR assumptions will also be used when assessing a signal across tumors within a group,

Subsequent Monotherapy Expansion

Based on totality of data obtained from the Initial Expansion, up to 126 subjects may be enrolled in the Subsequent Expansion cohorts with an expanded set of tumor types within and across groups (Table 8.1-3).

	signai	signal assessment when guided by a 2-stage design					
Tumor Cohort and Group	Target ORR %	SOC ORR %	Stage 1 / Total N	Stage 1 Res Futility/ Efficacy Boundary	Stage 2 Res Futility/ Efficacy Boundary	FPR/FNR (%)	
FUSION PROTEINS							
DHL	50	10	5/9	0/2	2/3	10/10	
NMC	50	10	5/9	0/2	2/3	10/10	
ES	35	10	5/9	0/2	1/2	20/20	
BL	50	10	5/9	0/2	2/3	10/10	
BRD AMPLIFICATI	ONS						
TNBC	50	10	5/9	0/2	2/3	10/10	
OC w BRD amplifications	50	10	5/9	0/2	2/3	10/10	
NEPC	50	10	5/9	0/2	2/3	10/10	
MYC AMPLIFICATI	ONS						
Non-GC-DLBCL	35	10	5/9	0/2	1/2	20/20	
OC w MYC amplifications	35	10	5/9	0/2	1/2	20/20	
UCS	35	10	5/9	0/2	1/2	20/20	
AR AMPLIFICATIO	NS						
CRPC	35	10	5/9	0/2	1/2	20/20	

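### CRPC entry criteria (2) and (4) are joined without 'or', so read literally they require both AR and MYC amplification, against their own wording and the protocol's rationale sections

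*Protocol*

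**What the plan says.** Protocol Section 3.3.1, item 2a, asks for a confirmed diagnosis of "one of the following malignancies for participation in the study and meet the other criteria listed". Under CRPC (item ix) the numbered criteria include:

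- (2) "Detected AR amplification in tumor cells (with or without MYC amplification"
- (4) "Detected MYC amplification in tumor cells (with or without AR amplification"

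No 'or' stands between them. The same list writes alternatives out where it means them: ovarian criterion (5) uses 'and/or', and NSCLC criterion (3) uses 'or'.

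Item xiii covers "Double-hit lymphoma (DHL) or non-germinal center subtype of diffuse large B-cell lymphoma (non-GC-DLBCL" in one numbered list. Criterion (1) is "FISH-confirmed rearrangement of MYC and of BCL2 or BCL6 DHL". Criterion (4) is "IHC confirmed CD 10-, BCL6- DLBCL, or CD10-, BCL6+ and MUM1+ DLBCL", followed by a sentence tying it to the diagnosis of non-GC-DLBCL. Criterion (4) sets no MYC condition.

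Elsewhere, Section 1.1.8 (repeated in SAP Section 1) makes TNBC, non-GC-DLBCL and CRPC eligible with any of the BRD, MYC or AR amplifications or overexpressions. Section 1.1.9 describes the eligible CRPC subjects as AR-amplified. CRPC appears only under the AR group, and non-GC-DLBCL only under the MYC group, in Protocol Tables 3.1.2.4-1 and 8.1-2 to 8.1-4 and in SAP Tables 2.1-1 and 5.2-1. A note to Table 8.1-2 adds: "Tumor ORR assumptions will also be used when assessing a signal across tumors within a group".

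**The concern.** Three CRPC rules coexist: both alterations (literal Section 3.3.1), any alteration (Section 1.1.8), and AR-amplified (Section 1.1.9). Section 3.3.1 is what sites apply. Section 3.3 allows no exceptions, and Section 3.3.2 closes by insisting that every criterion be met in full. A site reading the list as written would turn away CRPC patients with AR amplification alone and those with MYC amplification alone.

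If the items are meant as alternatives, a smaller issue follows. MYC-only subjects would sit in a cohort labelled by AR amplification, while the non-GC-DLBCL cohort is labelled by MYC amplification but entered on cell of origin. Section 1.1.8 says the study may help show whether activity depends on specific alterations, so a reader of the cohort results needs to know who carried what.

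**Working it through.** **Plan's own figure.** For CRPC, Table 8.1-2 gives target ORR 35%, standard-of-care ORR 10%, 5 then 9 subjects, stop at 0 of 5, positive at 2 or more of 9, and FPR/FNR 20/20. (The SAP Section 5.2 text states one failure limit of 2 or fewer of 9 for all cohorts; I use the table values.)

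P(positive) = P(X9 ≥ 2) − P(X5 = 0) × P(X4 ≥ 2)

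- At 10%: 0.2252 − 0.5905 × 0.0523 = 0.194, so FPR is 19.4%.
- At 35%: 0.8789 − 0.1160 × 0.4370 = 0.828, so FNR is 17.2%.

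Both fit 20/20 as ceilings. No error in the design figures is alleged.

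**Eligible share of CRPC.** Inputs from Section 1.1.8: "Approximately 67% of CRPC patients harbor AR amplification, and 25% to 30% harbor both MYC and AR amplifications", and MYC amplification in 41%.

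| Reading of (2) and (4) | Share of CRPC | Tested to fill 9 (9 ÷ share) |
|---|---|---|
| Both required | 25-30% | 30-36 |
| AR required | 67% | about 13.4 |
| Either suffices: 67 + 41 − (25 to 30) | 78-83% | 10.8-11.5 |

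The last column counts the biomarker criterion alone.

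**Make-up of the cohort if 'or' is meant.**

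- MYC-only, as a share of all CRPC: 41 − 30 = 11% to 41 − 25 = 16%.
- As a share of eligible CRPC: 11/78 = 14.1% to 16/83 = 19.3%.
- Expected among 9: 9 × 0.141 = 1.3 to 9 × 0.193 = 1.7.
- Chance of at least one in 9: 1 − (1 − 0.141)^9 = 75% to 1 − (1 − 0.193)^9 = 85%.

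**Would counting only AR-amplified subjects be better?** Dropping one or two MYC-only subjects leaves 8 or 7. Keep stage 1 at 5 and the same boundaries, at a true ORR of 35%:

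- n = 8: 0.8309 − 0.1160 × 0.2818 = 0.798, so FNR is 20.2%.
- n = 7: 0.7662 − 0.1160 × 0.1225 = 0.752, so FNR is 24.8%.

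Both exceed the stated 20%.

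**The case against.** The strongest reply is that the intent is plain. The two parentheses make no sense under 'and', Section 1.1.8 says any alteration, and the summary of changes records an added rationale for MYC amplification in CRPC. Assignment in Part 2 is central through IRT, after the biomarker result, so a strict exclusion might be caught. Section 1.1.9 says AR-positive subjects are eligible without saying that only they are. All of this stands as evidence for 'or'. It does not change what Section 3.3.1 tells a site to apply.

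The documents do not support several stronger readings that a reader might infer:

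- *That the plan both demands two alterations and mixes MYC-only subjects into the AR cohort.* These exclude each other. If both are required, no MYC-only subject can enter.
- *That the lymphoma list is equally contradictory.* The 'or' in its heading and the disease named in (1) and after (4) largely settle it. What remains is drafting.
- *That non-GC-DLBCL is misplaced in the MYC group.* Section 1.1.9 characterizes the disease by MYC overexpression. The label is loose and entry sets no MYC condition, but grouping by disease biology is a sponsor's choice.
- *That the mixture distorts a pooled AR signal.* CRPC is the only tumor in the AR group in every table, so nothing is pooled across tumors there. The two-stage rule applies per cohort, and the visible SAP efficacy summaries are by treatment and tumor type.
- *That the plan has no analysis by alteration.* Parts of both documents are redacted, so this cannot be said.

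**Conclusion.** The CRPC entry rule is wrong as written and needs correcting. Which reading holds moves the eligible share of CRPC from 25-30% to 67% or 78-83%, on the TCGA prevalences that the protocol cites. The enrolled, pretreated population may differ, and the screening counts ignore every other criterion.

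The labelling issue is secondary and depends on the answer. Under 'or', 1 to 2 of 9 CRPC subjects would be expected to carry MYC amplification only, and non-GC-DLBCL subjects may enter without a MYC finding. Section 3.3.1 item 2d and Table 5.1-1 exempt neither tumor type from the adult Part 2 screening test, so status will be known and can be displayed.

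A reader might go further and want the AR decision based on AR-amplified subjects alone. The documents do not call for that, and at 8 or 7 subjects the FNR passes the stated 20%. If MYC-only tumors were assumed to respond at 10% (the documents give no such figure), the undivided cohort of 9 would have power of 74.9-77.2%, against 75.2-79.8% after dropping two or one subjects. That is no clear gain.

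**What to change.** 1. In Section 3.3.1 item ix, join criteria (2) and (4) with 'or', as their parentheses and Section 1.1.8 imply, and reword Section 1.1.9 to match. If the sponsor intends another rule, all four places still have to be reconciled to it.
2. In item xiii, mark criterion (1) as applying to DHL only and (4) to non-GC-DLBCL only.
3. Leave the nine-subject cohort decision rules unchanged.
4. In the SAP, add a descriptive display of CRPC responses by AR/MYC status and of non-GC-DLBCL responses by MYC status, unless a redacted section already provides one.

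Cost: a wording amendment and one descriptive table, using screening results already required. The sample size does not change.
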